6.1.2 Blinding

Blinding the test persons and/or the examiners is not possible with regard to the intervention.

The implementation of the intervention and the measurements of the primary and secondary outcome parameters are not carried out by the same examiner.

SUPSI

The blinding of the statistician can be guaranteed, who has no access to the personal data of the test persons and is not present during the data collection.

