	
Measurement procedure
 
This is followed by the 1st measurement (pre-mobilisation). Afterwards, the mobilization pressure is built up individually up to the tolerance limit of the test subject so that a displacement of the patella caudally takes place (2nd measurement). The maximum deflection of the patella to the reference point is determined and the device settings are noted. As described above, further measurements are carried out according to the following scheme: after 10 mobilisations (3rd measurement), after 20 mobilisations (4th measurement), after 30 mobilisations (5th measurement), after 50 mobilisations (6th measurement).
 
The device settings are kept the same for all measurements per subject.

	
Objective Displacement
 
The displacement of the patella due to mobilization is objectified by means of an imaging ultrasound device. In a second step, the distance of the patellar displacement is evaluated using the ultrasound images using special software (OsiriX, www.Osirix-viewer.com).

	
Subjective information on general well-being
 
After each measurement interval, the subjects report their subjective well-being using a visual analogue scale (VAS). The scale is from "0" (maximum well-being) to "10" (maximum discomfort) in cm-steps.

	
Further processing of the data
 
Microsoft Excel from Windows is used for data pooling and the graphical representation of the end data.

Measurements and procedures:	For this study, we use a device (Patello, Srm-Projects GmbH, Chur) that mobilizes the patella by apparatus, passively and continuously.
Control Intervention (if applicable):	There is no control intervention.
Number of Participants with Rationale:	We limit the number of subjects to $n = 30$. According to the g*power calculation, this gives us an effect size of 0.68 with a power of 0.95.
Study Duration:	June 2018 - December 2018
Study Schedule:	June 2018: planned start of measurements December 2018: planned end of measurements

SUPSI

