8.2.2 Control intervention

There is no control intervention.

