9.1.2 Measurement of primary outcomes

The ultrasound probe is used to record one reference point on the patella and one on the thigh (lateral epicondyle femoris) and store it as an image. After caudal mobilization, the same reference points are recorded and again stored as an image. This process is performed before the first and after each mobilization interval (1st-6th measurement). With the OsiriX software, the DICOM images obtained can be analyzed and evaluated. The distance of the displacement of the patella is shown in mm and transferred to the data sheet.

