10 STATISTICAL METHODS

10.1 Hypotheses & Factors

Mobilization of the patella in the caudal / cranial direction by the patello – repetitive mobilizations versus one-time mobilization Objective displacement of the patella:

H0 The patella does not shift significantly more during repetitive mobilizations than during a single mobilization by the patello.

H1 The patella shifts significantly more during repetitive mobilizations than during a single mobilization by the patello.

Subjective well-being of the subject:

H0 Subjective well-being does not change significantly more with repetitive mobilizations than with a single mobilization by the patello.

H1 Subjective well-being changes significantly more with repetitive mobilizations than with a single mobilization by the patello.

A 2-factor analysis is carried out.

Factor 1: Intervention

Factor 2: Time intervention: Start (pre-intervention, 1st measurement), after a single mobilization (2nd measurement), after 10 (3rd measurement), after 20 (4th measurement), after 30 (5th measurement), after 50 mobilizations (6th measurement)

Sample size

The planned sample size is $n = 30$ subjects. This size is expedient, time-wise and financially feasible for the study.

10.2 Criteria for the statistical use of data in the case of incomplete data sets

A complete mobilization interval must be completed for the data to be included in the study. If a mobilisation interval (e.g. interval '20 mobilisations', but termination after 15 mobilisations) has to be interrupted, only the previously collected complete mobilisation interval data can be used. This ensures that all data remains homogeneous and comparable. No substitute is sought for the missing mobilization interval data.

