10.3.2 Primary Analysis

The statistical data analysis is carried out by the statistician after completion of the data collection of the entire project.

Repeated measures analysis of variance (MANOVA) A 2-factor analysis is performed.

Factor 1: Intervention

Factor 2: Time intervention: Start (pre-intervention, 1st measurement), after a single mobilization (2nd measurement), after 10 (3rd measurement), after 20 (4th measurement), after 30 (5th measurement), after 50 mobilizations (6th measurement)

The significance level is set at $P < 0.05$, and the statistical data analysis is carried out with SPSS V. 24.

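### The plan specifies no masking for the off-line reading of the stored ultrasound images, so reader expectation could bias the comparison of single with repeated mobilisation

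*Combined protocol and SAP*

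**What the plan says.** On blinding, section 6.1.2 of the protocol states: "Blinding the test persons and/or the examiners is not possible with regard to the intervention". It then gives two safeguards. The person who applies the device is not the person who measures the outcomes, and the statistician is blinded in the sense of having no personal data and not attending the sessions. Section 6.2 says the opposite about the statistician. Section 6.1.3 rules out further methods.

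On the primary outcome, section 9.1.2 has an image stored at each of the six measurements, showing a point on the patella and one on the lateral femoral epicondyle. The synopsis places the measurement of distance after this: "In a second step, the distance of the patellar displacement is evaluated using the ultrasound images using special software". Section 9.1.2 adds: "With the OsiriX software, the DICOM images obtained can be analyzed and evaluated". Section 11.2.1 confirms that the OsiriX result in mm goes onto the data sheet. Section 9.2.3, however, also has the maximum deflection determined during the session.

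On the comparison, the alternative hypothesis in section 10.1 reads: "The patella shifts significantly more during repetitive mobilizations than during a single mobilization by the patello". Section 8.2.2 states: "There is no control intervention".

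The coding described in sections 1.7 and 11.1.1 protects the subject's identity. No section mentions hiding the interval or the day from the image reader, changing the order of the files, or repeating a reading.

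**The concern.** Reading a distance from an image requires someone to place two landmarks. According to the synopsis, measurements 2 to 6 are all recorded in the caudal position, and section 3.6 keeps the device settings fixed within a day. The hypothesis in section 10.1 therefore rests on differences between images that should look much alike. The protocol also says which way it expects the result to go: section 3.6 looks for a positive effect of repetition.

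A reader who knows that one image follows 50 mobilisations and another follows one could place the landmarks slightly differently without intending to. In a controlled trial, a shift of this kind that was equal in both arms would cancel. Here nothing cancels it, and it adds directly to the within-subject difference.

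Section 6.1.2 considers blinding only during the session, where it is indeed impractical. It does not consider the later reading step, where blinding is feasible because the files already exist.

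**Working it through.** **1. Do the existing safeguards reach the reader?**
- Separate examiners (6.1.2): this divides the tasks but does not conceal the measurement number.
- Statistician blinding (6.1.2): this takes effect once the distances are on the data sheet, and a single-arm study has no allocation to hide. Section 6.2 denies it in any case. That may be a translation slip, since section 6.3 makes sense only if its word for blinding means unblinding.
- Identity coding (1.7, 11.1.1): this covers who the subject is, not which interval or day an image belongs to.
- Anything else: excluded by 6.1.3.

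None of these reaches the reading step.

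**2. The plan's own figure.** The synopsis limits the study to 30 subjects and says that "this gives us an effect size of 0.68 with a power of 0.95". The type of effect size and the sidedness are not stated. Reading 0.68 as the mean paired difference divided by its SD, with a two-sided 0.05 paired t test:
- noncentrality = 0.68 × √30 = 3.72; df = 29; critical t = 2.045
- power = P(|t| > 2.045) = 0.949, which agrees with 0.95.

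A one-sided test gives 0.977, which does not agree. The two-sided paired t test is therefore used below.

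**3. Effect of a reading shift.** Assume one paired difference per subject (repeated minus single), no true effect, and a systematic reading shift of b SDs of that difference. The false-positive rate is P(|t| > 2.045) with df = 29 and noncentrality b × √30.

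| Assumed shift b | b × √30 | False-positive rate, two-sided 0.05 |
|---|---|---|
| 0.1 | 0.548 | 0.083 (8%) |
| 0.2 | 1.095 | 0.185 (19%) |
| 0.3 | 1.643 | 0.355 (36%) |

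If the directional hypothesis were tested one-sided at 0.05, the same shifts would give 13%, 28% and 48%.

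**4. Scale.** An observed difference is significant from 2.045 / √30 = 0.373 SD upwards, so a pure reading shift of about 0.37 SD produces a false positive about half the time. The documents give no SD in mm. If the SD of the paired difference were 0.5, 1 or 2 mm, that shift would be about 0.19, 0.37 or 0.74 mm.

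**5. What these figures do not cover.** Section 10.3.2 plans a repeated-measures analysis over all six time points, including the pre-mobilisation image. I simulated a six-level repeated-measures F test with n = 30, independent errors and an assumed pre-to-post displacement of 1 or 2 SD of the paired difference. It was significant in every run, whether the reading bias was 0, 0.2 or 0.3 SD. Displacement by the device drives that result, so the rates in step 3 apply only to the single-versus-repeated contrast.

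**6. Effect of masking.** The sample size stays at 30 and the power at 0.949. If the masking holds, the false-positive rate from interval-related reading bias returns to 0.05.

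**The case against.** The strongest reply is that the plan is silent about the reader rather than wrong. The sentence in 6.1.2 concerns subjects and examiners in relation to the intervention. No section says who reads the images or what that person knows. This stands: a reader of the protocol might infer that the images are definitely read with the interval in view, but the documents support only that no masking is specified. Since 6.1.3 excludes other methods, the gap still needs closing.

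It would also be tempting to say that 6.1.2 offers nothing except statistician blinding. That is not so. The separate-examiner rule is a real, partial safeguard, although it does not hide the interval.

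A third reply is that the error rates are not those of the planned test and that the shifts are invented. Both parts stand. The rates illustrate the contrast that section 10.1 sets up but section 10.3.2 does not specify, and no document figure shows whether 0.1 to 0.3 SD is likely.

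Finally, masked reading cannot be complete. The examiner who places the probe and chooses the frame can still know the interval, and the pre-mobilisation image may be recognisable. The first limit stands in full. The second matters less, because the contrast in 10.1 starts from measurement 2.

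**Conclusion.** The concern holds as an unaddressed, avoidable route for bias. The primary outcome is read from stored files, nothing in the plan conceals the measurement number at that step, and the single-arm design gives no protection. Under the assumptions in the working, shifts of 0.1 to 0.3 SD would raise the false-positive rate of the single-versus-repeated contrast from 5% to between 8% and 36%.

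A reader might go further and infer that a positive repetition result would be an artefact, or that the main analysis has a false-positive rate of 36%. The documents support neither. They give no reading error, they do not say what the reader knows, and the six-level test answers a different question. The stated power is not in dispute. Confidence is medium. The change is worth making because it is cheap, not because bias has been shown.

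**What to change.** In sections 6.1.2 and 9.1.2:

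1. Name the off-line OsiriX distance as the primary value, and say what the deflection determined in session (9.2.3) is used for.
2. Before reading, have an existing team member other than the reader remove identifiers, time stamps and measurement numbers from the DICOM files (30 subjects × 2 days × 6 = 360), assign codes, and hold the key.
3. Shuffle interval and day within each subject, 12 images at a time. Shuffling across subjects would take away the subject's other images, which help the reader to find the same reference points, and could add measurement error.
4. Enter distances against the code, and join the key only after the readings are locked.
5. State that the monthly presentation of results in section 11.4 must not unmask the reader.
6. Reconcile sections 6.1.2 and 6.2 on the statistician.

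The cost is a small coding task and reading in batches. No subjects, visits or images are added. Masking to day mainly serves the objective on lasting or cumulative effects in section 4.3, because day is not a factor in section 10.3.2. The protocol should state two remaining limits: the pre-mobilisation image may be recognisable, and bias from probe placement or choice of frame is not removed.

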6.1.3 Other Methods

No other methods are used.

6.2 Procedure for unblinding (code break)

There is no provision for the statistician to be blinded.

6.3 Procedure for unblinding (code break)

Blinding is only permitted if an unforeseen incident or medical problems occur in a subject during or after completion of study participation, which may be attributable to participation in the study.

SUPSI

7 POPULATION STUDIES

7.1 Inclusion Criteria

Table 3: Overview of inclusion and exclusion criteria

Inclusion Criteria	Exclusion criteria

- Adults aged 18 to 30 Years- No surgical interventions and/or current complaints (pain at rest or during exertion) on the musculoskeletal apparatus in the area of the lower extremities- closed, intact skin conditions in the knee and thigh area- Don't be afraid of the intervention	
- Adolescents and adults over 30 years of age- Surgical interventions and/or current complaints (pain at rest or during exertion) on the musculoskeletal Apparatus in the area of the lower extremities- no closed, intact Skin conditions in the knee and thigh area- Fear of intervention

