3.7 Risk / Benefits

The possible occurrence of risks from the use of the Patello is to be assessed as small: short-term skin irritations and/or paraesthesia could occur.

The subjects do not benefit from participating in the study. The study serves to prove the effectiveness of the Patello device. If this is the case, the device can be used in the rehabilitation process of patients with the above-mentioned knee joint problems.

Justification of the choice of population

This series of studies will be conducted with healthy adults to assess the extent of the Quantify displacement of the kneecap by means of the patello.

Table 1: Overview of inclusion and exclusion criteria

Inclusion Criteria	Exclusion criteria

- Adults aged 18 to 30 Years- No surgical interventions and/or current complaints (pain at rest or during exertion) on the musculoskeletal apparatus in the area of the lower extremities- closed, intact skin conditions in the knee and thigh area- Don't be afraid of the intervention	
- Adolescents and adults over 30 years of age- Surgical interventions and/or current complaints (pain at rest or during exertion) on the musculoskeletal Apparatus in the area of the lower extremities- no closed, intact Skin conditions in the knee and thigh area- Fear of intervention

The test subjects are comprehensively informed about the course of the study and possible risks before they are accepted to participate in the study. You will also receive the information in written form and have the opportunity to ask questions if anything is unclear. The declaration of consent explains to them what their rights and obligations are when participating. In addition, they are informed that they may withdraw from participation at any time without giving reasons, without incurring any disadvantages as a result.

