8 STUDY INTERVENTION

8.1 Medical Device ID

8.1.1 Intervention product

The Patello is a device for "Continuous Passive Motion" (CPM) of the patella. It grips the kneecap and mobilizes it in the caudal / cranial direction. Among other things, the system supports rehabilitation in the event of limited mobility of the knee joint, such as knee surgery (see Chapter 3).

The most important components of the Patello are highlighted in the following image:

[figure not shown]

Fig . 7: Patello

1. Knee brace
2. Switch panel
 - a. Slot for power plug
 - b. On/Off Switch
 - c. Reset button
3. Knee brace
4. Handheld control unit with emergency stop switch
5. Essay
 - a. Patellar Gripper
 - b. Display
 - c. Air cushion

SUPSI

6. Lifting columns

Handling Patello

1. To turn on the Patello:

Press the red on/off switch on the switch panel. The device will start initializing. After initialization is complete, the device switches to teaching mode (visible on the display).

2. Moving the grippers:

Press the "Grip" button on the hand control unit. The grippers move together until they grasp the patella from caudal and cranial.

Fig. 8: Handheld control unit

3. Operate and release the emergency stop: Switch the emergency stop toggle switch on the handheld control unit to "O". The grippers relax and the display shows the emergency stop mode. Switch the emergency stop toggle switch back to "I". Press the reset button on the switch panel.

Fig. 9: Emergency stop toggle switch

Securing the test subjects

Through the screening process (filling out the health questionnaire with examination of the inclusion and exclusion criteria), only subjects who are suitable for participation in the study are recruited. In this way, at-risk test subjects are identified at an early stage and are not recruited/included in the study.

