8.3 Dosage, application modification

In a first phase, the device settings (contact and mobilization pressure of the patello) are adjusted based on the well-being of the test subject. The mobilization pressure is built up individually to the tolerance limit so that a displacement of the patella takes place. The selected intensities are noted and maintained during all measurements per subject.

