8.6 Preventive measurements

The questionnaire determines the eligibility to participate in the study by recording the inclusion and exclusion criteria.

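### Section 8.1.1 says screening keeps at-risk volunteers out, but the listed criteria would admit a pain-free, never-operated volunteer with known patellar instability or reduced sensation at the knee

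*Combined protocol and SAP*

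**What the plan says.** The eligibility criteria appear with the same content in the synopsis, in section 3.7 and in section 7.1: age 18 to 30, intact skin at knee and thigh, no fear of the procedure, and "No surgical interventions and/or current complaints (pain at rest or during exertion) on the musculoskeletal apparatus in the area of the lower extremities". The bracket explains complaints as pain.

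On how the criteria are applied, section 8.6 states: "The questionnaire determines the eligibility to participate in the study by recording the inclusion and exclusion criteria". Sections 7.2 and 9.2.1 add that a volunteer who meets the inclusion criteria has passed screening and is admitted. Section 8.1.1 concludes: "In this way, at-risk test subjects are identified at an early stage and are not recruited/included in the study".

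On the intervention, section 8.3 states: "The mobilization pressure is built up individually to the tolerance limit so that a displacement of the patella takes place". Section 9.2.3 and the synopsis repeat the rule. No numeric maximum of force, pressure or displacement is given. Under section 3.6 the settings are then held for all six measurements of the day, up to 50 mobilizations, on each of two days.

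On safeguards, sections 3.2 and 8.1.1 describe a hand-held emergency stop. Section 5.2 lets the examiner stop on the basis of what the subject feels and expresses, and lets the subject stop at will. Section 9.4.1 ends participation after a side effect. Section 3.7 names the expected risks: "short-term skin irritations and/or paraesthesia could occur".

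**The concern.** The assurance in section 8.1.1 is wider than the criteria behind it. Nothing listed asks about patellar instability, an earlier dislocation treated without surgery, or loss of sensation around the knee. The device displaces the patella, and the pressure is raised until the subject signals the limit of tolerance. In a person with reduced sensation that signal is unreliable. In a person with a known unstable patella, the study displaces a structure whose stability was never asked about, although section 3.1.3.2 itself describes patellar movement as controlled by a finely balanced ligament system.

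Screening also carries more weight here than usual. The complete device is not CE certified (synopsis, section 9.4). The authors know of no earlier study of this kind of mobilization (section 3.4). No safety parameters are collected beyond the health questionnaire (section 9.1.5), and no safety analysis is planned (section 10.3.5). Paraesthesia is a named possible effect, yet no sensory status at entry is described, so an existing deficit could not readily be told apart from a device effect.

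There is a smaller question of validity. Section 3.7 justifies the sample as healthy adults in whom displacement is to be quantified, and an unusually mobile patella would enter that estimate.

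**Working it through.** **The plan's own figure.** The synopsis fixes the sample ("We limit the number of subjects to" 30) and states that "this gives us an effect size of 0.68 with a power of 0.95". The test family and sidedness are not given. Assuming a paired t-test at two-sided 0.05, the noncentrality is 0.68 × √30 = 3.72 on 29 degrees of freedom, and the power is 0.949. The figure reproduces. Only n = 30 is used below; nothing here depends on the effect size.

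**Step 1: a test case against the criteria.** Take a 24-year-old volunteer who once dislocated a patella, was treated without surgery and has no pain. A second volunteer, also pain-free and unoperated, has reduced sensation over the thigh.

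| Criterion (sections 3.7, 7.1, synopsis) | Known instability | Reduced sensation |
|---|---|---|
| Age 18 to 30 | met | met |
| No lower-limb surgery | met | met |
| No current complaints (glossed as pain) | met | met |
| Intact skin at knee and thigh | met | met |
| No fear | met | met |
| Admitted under sections 7.2 and 9.2.1 | yes | yes |

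**Step 2: what limits the pressure.** Sections 8.3 and 9.2.3 name one limit, the subject's tolerance. The emergency stop (sections 3.2, 8.1.1) and the rules in sections 5.2 and 9.4.1 end a session or a participation. None sets an upper bound on pressure, and the examiner's rule in section 5.2 again relies on what the subject feels and expresses.

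**Step 3: chance of enrolling such a person.** The documents give no prevalence, so p is an assumption. With 30 independent subjects, P(at least one) = 1 − (1 − p)^30.

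- p = 1%: 1 − 0.99^30 = 0.260
- p = 2%: 1 − 0.98^30 = 0.455
- p = 5%: 1 − 0.95^30 = 0.785

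**Step 4: effect on the results.** Suppose one knee moves 10 mm more than the rest (assumed; the documents give no range). The mean displacement of 30 rises by 10/30 = 0.33 mm. The hypothesis in section 10.1, however, compares repeated with single mobilization in the same subject. If subject i carries a constant offset b at measurements 2 to 6, the difference between, say, measurements 6 and 2 is (μ6 + b) − (μ2 + b) = μ6 − μ2, and the offset cancels. Only the descriptive mean displacement is affected.

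**The case against.** The best case for the plan has four parts.

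1. **The questionnaire is not in the documents.** Section 8.6 says that it records the criteria, not that it records nothing else. Section 7.2 gives it the wider role of clarifying suitability, and the term at-risk is nowhere defined. A reader might infer that the assurance in section 8.1.1 is false; the documents do not go that far. They show only that the listed criteria do not support it. This stands, and the conclusion is worded accordingly.

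2. **Other safeguards exist.** A reader might infer that nothing protects the subject except tolerance. That is wrong: there is an emergency stop, the examiner and the subject may each stop, and a side effect ends participation. These belong in any fair account. They are ways to stop, however, and not limits on pressure.

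3. **The mechanism is partly unproven.** The device moves the patella cranially and caudally, and section 3.1.3.2 distinguishes longitudinal from transverse restraint. Nothing in the documents shows that a past dislocation increases caudal travel. This stands for instability, where the case is one of precaution. It does not touch the sensory case, where a limit based on sensation is unreliable by its own logic. Paraesthesia as a listed device effect is not evidence of how common an existing deficit is.

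4. **The figures are illustrative.** The prevalences are assumed and pool different conditions. This stands.

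**Conclusion.** The concern holds as an inconsistency between the assurance in section 8.1.1 and the criteria and admission rule in sections 7.1 and 7.2. Followed as written, the plan would admit volunteers with known patellar instability or known reduced sensation, and in the latter the only stated limit on pressure cannot be relied on. It should be corrected, chiefly on safety grounds.

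The size is uncertain. The 26% to 79% range rests entirely on assumed prevalences of 1% to 5% and on independence between subjects. A reader might take it as a risk of injury; it is only the chance of enrolling at least one such person, and the documents offer no link from enrolment to harm.

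A reader might also infer that the primary comparison is biased. It is not, so long as the extra laxity is a constant offset. The effect is then confined to the mean displacement, at 0.33 mm for one knee with an assumed excess of 10 mm.

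**What to change.** Reconcile section 8.1.1 with sections 7.1, 7.2, 8.3, 8.6 and 9.2.3. Add two screening items to the criteria tables in sections 3.7 and 7.1, to the synopsis and to the existing health questionnaire:

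1. known patellar instability or dislocation;
2. known reduced sensation at the knee or thigh.

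The study physician should set the final wording. If the questionnaire already asks about either, state this in sections 7.1 and 8.6, so that the criteria match what is screened. No change to device pressure or to the stopping rules is proposed.

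A blanket exclusion of any previous knee injury is not recommended: without a limit on severity or time it would remove volunteers with an old sprain or bruise.

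The cost is two questions on a form that is already filled in, and probably a few more screen failures. The documents give neither the size of the internal recruitment pool nor the frequency of these histories, so the number cannot be estimated.
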